2.2 Study Design

The PEDAL study is designed as a pragmatic, multicentre RCT (with an internal pilot study) with two treatment arms: intra-dialytic exercise training plus usual care maintenance haemodialysis (EXHD) versus usual care maintenance haemodialysis (UCHD). Participants' QOL and functional limitations will be assessed prior to treatment randomisation and after 6, 9 and 15 months. The primary endpoint will be after 6 months with additional follow-up at the end of the intervention (9 months) and again 6 months after the end of the intervention period. It will be impossible to blind the "treating" physiotherapy assistants or the participants and thus the study will undertake blinded outcome assessment and analysis. We propose to recruit participants to the PEDAL study from all eligible adult prevalent HD patients who have been receiving maintenance HD for more than 3 months. These will be recruited from UK (outpatient in-centre) HD units. Recruitment for the trial will take place over a 21-month period between November 2014 and July 2016 in HD units

based in 10 sites across 5 regions of the United Kingdom (London, Birmingham/West Midlands, East Midlands, North Wales & North West England, and Central Scotland)

[figure not shown]

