4.3 Screening for Eligibility

After informed consent is obtained and eligibility by all the criteria (protocol sections 3.2 & 3.3) confirmed, study assessments as outlined in section 4.6 will be performed.

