4.6 Schedule of Assessment for each visit

Table 2. The range and phasing of PEDAL study assessment procedures

ASSESSMENT PROCEDURES					
	Timeline ± 1 week				
	Screening	Baseline	6 months	9 months	15 months
Informed Consent	X				
Inclusion/Exclusion Criteria	Х				
Medical History/Demographics	Х				
Adverse Events Recorded		Х	Х	Х	Х
Review/Record Medication		Х			
Anthropometric Measurements					
Height		Х	Х	Х	Х
Weight		Х	Х	Х	Х
Body Mass Index		Х	Х	Х	Х
Waist-to-Hip ratio		Х	Х	Х	Х
Quality of Life (and symptom					
burden) Assessments)					
* KDQOL		Х	Х	Х	Х
* EQ5D		Х	Х	Х	Х
Cardiovascular Assessments					
Resting Heart Rate		Х	Х	Х	Х
Resting Blood Pressure		Х	Х	Х	Х
Pulse Wave Velocity		Х	Х	Х	Х
Augmentation Index		Х	Х	Х	Х
Functional Capacity					
Measurements					
Peak Aerobic Capacity		Х	Х	Х	Х
(VO ₂ peak and/or Peak power output)					
Sit-to-Stand 60		Х	X	Х	Х
Functional Mobility (10mTUG)		Х	Х	Х	Х
* DASI questionnaire		Х	Х	Х	Х
* Tenetti Falls Efficacy Scale		Х	Х	Х	Х
Habitual Physical Activity					
GT3X Accelerometer		Х	Х	Х	Х
International Physical Activity		Х	Х	Х	Х
Questionnaire					
Routine Clinical Chemistry					
URR(5)		Х			
Blood lipid levels		X			
(LDL, HDL, triglyceride levels)					
Hb (and ESAs)		Х	Х	Х	X
HBA1c		X			,,
CRP		X			
Bicarbonate		X			
Phosphate		X	Х	Х	Х
Parathyroid hormone		X	X	X	X
		l			
Note: * o	denotes patient	t-reported out	come.		

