5.0 Safety

5.1 Definitions

Unexpected events that have not been defined as endpoints should be classified as either an SAE or AE depending on their severity. There is no requirement to report AE's. All SAEs must be recorded from the time at which the randomisation of the participant has occurred until the last study visit. The member of the research team should ask about the occurrence of SAEs at every visit during the study. Open-ended and non-leading verbal questioning of the participant should be used to enquire about AE/SAE occurrence. Participants should also be asked if they have been admitted to hospital, had any accidents, used any new medicines or changed concomitant medication regimens. If there is any doubt as to whether a clinical observation is an SAE, the event should be recorded. However, common symptoms in dialysis patients such as headache, nausea, itching etc., as well as infections not requiring hospitalisation, will not be recorded. Each initial SAE will be considered for severity, causality or expectedness and may be reclassified as a serious event or reaction based on prevailing circumstances.

A serious adverse event (SAE) is any AE that:

- results in death;
- is life threatening (i.e. the subject was at risk of death at the time of the event; it does not refer to an event which hypothetically might have caused death if it were more severe):
- requires hospitalisation or prolongation of existing hospitalisation;
- results in persistent or significant disability or incapacity;
- is a congenital anomaly or birth defect.

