5.3.2 Assessment of causality

Probable: A causal relationship is clinically / biologically highly plausible and there is a plausible time sequence between onset of the adverse event and the exercise intervention.

Possible: A causal relationship is clinically / biologically plausible and there is a plausible time sequence between onset of the adverse event and the exercise intervention.

Unlikely: A causal relationship is improbable and another documented cause of the adverse event is most plausible.

Unrelated: A causal relationship can definitely be excluded and another documented cause of the adverse event is most plausible.

6. Statistical Considerations

Analysis and reporting of this trial will be based on Consolidated Standards of Reporting Trials (CONSORT) guidelines with the analyses conducted on an intention-to-treat basis. Descriptive statistics of clinical and socio-demographic variables at baseline will be presented. All treatment comparisons will be adjusted for the minimisation variables (diabetic status, age and gender).

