Appendix 1 - Estimated time required to conduct principal study outcome assessments

Estimated time required to conduct principal study outcome assessments	Estimat ed time (mins)	When outcome is to be measured ±1 week			
	(IIIIII)	Baseline	6 months	9 months	15 months
Anthropometric Measurements (height, weight, BMI, waist:hip)	5	X	X	X	X
BP and resting heart rate Arterial stiffness (PWV &AI)	30	X	X	X	X
Functional mobility (10mTUG)	5	X	X	Х	X
DASI questionnaire	5	X	X	X	X
Sit-to-stand 60	5	X	X	X	X
Tinetti Falls Efficacy Scale	10	X	X	X	X
Quality of Life (KDQOL)	20	X	X	X	X
EQ5D	10	Х	Х	Х	X
Peak Aerobic capacity (Vo2 peak and/or peak power output) from graded exercise test	30	Х	Х	Х	Х
Physical activity measured by GT3X accelerometry	7 days	Х	Х	Х	Х
Routine clinical; chemistry – Hb, phosphate, PTH	during study period				

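### Mandatory SAE recording starts at randomisation, after the baseline graded exercise test, and other sections conflict with that start, so serious events from that test are not reliably captured

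*Protocol*

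**What the plan says.** Section 5.1 sets the window for SAEs: "All SAEs must be recorded from the time at which the randomisation of the participant has occurred until the last study visit". It also says that non-serious adverse events need not be reported, and that staff ask about SAEs at each visit.

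On the order of procedures, section 2.2 says: "Participants' QOL and functional limitations will be assessed prior to treatment randomisation and after 6, 9 and 15 months". Section 4.3 says that, once consent is obtained and eligibility confirmed, "study assessments as outlined in section 4.6 will be performed". Table 2 in section 4.6 lists peak aerobic capacity at baseline and at 6, 9 and 15 months. Appendix 1 describes it at the same four time points as "Peak Aerobic capacity (Vo2 peak and/or peak power output) from graded exercise test".

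Table 2 also has a row headed "Adverse Events Recorded", marked at baseline and at all three follow-up visits. Section 5.3 asks investigators to report every unexpected adverse event, serious or not, to the trials unit and gives no start time.

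In section 5.3.2 the probable and possible categories both depend on a "plausible time sequence between onset of the adverse event and the exercise intervention". The unlikely and unrelated categories rest on another documented cause.

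Section 8.1.1 recognises that exercise tolerance and functional capacity assessments, as well as the training, may cause adverse reactions. It adds that many patients will be elderly and may have many co-morbidities.

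**The concern.** A graded test to peak capacity is a trial procedure whose risk the protocol itself acknowledges. If the first such test comes before randomisation, the one sentence that sets a start for SAE recording leaves it out, while the assessment schedule appears to include it. Two sites could each follow the protocol and handle the same event differently: one records a hospital admission after the baseline test, the other does not. The person most likely to be missed is someone harmed at baseline who is then not randomised, because no later study visit exists at which to ask.

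The causality scale raises a related problem after randomisation. Both arms repeat the graded test at 6, 9 and 15 months, but relatedness is judged only against the exercise programme. A usual-care participant has no exposure to that programme, so harm from a test cannot be shown as related to the trial.

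At stake are oversight of participants and the trial's account of the risk of its own procedures.

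**Working it through.** The protocol states no figure to reproduce here. The check sets its passages side by side.

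**1. Order of events**

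| Step | Source |
|---|---|
| Consent and eligibility | 4.3; Table 2, screening column |
| Assessments listed in 4.6, including peak aerobic capacity | 4.3; Table 2, baseline column; Appendix 1 |
| Randomisation | 4.4; placed after the functional assessment by 2.2 |
| Mandatory SAE window opens | 5.1 |
| Graded test repeated at 6, 9 and 15 months | Table 2; Appendix 1 |

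Section 2.2 speaks of functional limitations and does not name the graded test. Table 2 lists peak aerobic capacity under functional capacity measurements at baseline, and section 4.3 puts the schedule's assessments directly after consent. That the test precedes randomisation is therefore a strong inference from passages that agree. The flow diagram is not available to confirm it.

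**2. What each passage implies for a serious event at the baseline test**

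| Passage | Is the event captured? |
|---|---|
| 5.1, start of window | No: it precedes randomisation |
| 5.1, enquiry at every visit | Possibly, but the next scheduled assessment is at 6 months and the event still predates the window. A person never randomised has no later visit |
| Table 2, adverse event row | Yes at baseline, but the row sets no reporting deadline or recipient |
| 5.3 | Yes if the event counts as unexpected; no start time is given |
| 5.2 | SAEs go to the trials unit within 7 days; only confirmed unexpected SAEs go on to the Sponsor, ethics committee and safety committee |

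The answers differ. Sections 5.2 and 5.3 turn partly on expectedness. Under 8.1.1, possible reactions to the tests are described in the patient information sheet, so a site could argue that such a reaction is expected.

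**3. Conflict on non-serious events**

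Section 5.1 removes any duty to report non-serious adverse events. Section 5.3 requires reports of unexpected events whether serious or not. Both cannot be followed.

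**4. Causality of an event caused by a follow-up test**

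- Usual-care arm: there is no exercise intervention, so probable and possible do not apply. The event goes to unlikely or unrelated, with the test as the other documented cause.
- Exercise arm: if the test is the cause, the same two categories apply. If the event is rated possible or probable, it is attributed to the training instead.

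In neither arm does the scale identify the trial assessment as the source.

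**5. Scale**

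Scheduled graded tests: 380 participants × 4 time points = 1,520. Tests before the 5.1 window opens: 380 × 1 = 380, and 380 / 1,520 = 25%. This counts scheduled tests, not events, and assumes that every participant completes all four. The protocol gives no event rate for testing and no number of people tested but not randomised, so neither can be sized.

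**The case against.** The case on the other side is substantial. Table 2 marks adverse events at baseline. Section 5.1 has staff ask about SAEs at every visit without limiting this to visits after randomisation. Section 5.3 has no start time. Section 5.2 makes the Chief Investigator responsible for prompt notification of findings that could harm participants, and section 8.1.2 promises monitoring throughout the trial. A careful site might well report a serious event at the baseline test.

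This defeats three stronger readings that a reader might infer:

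- That baseline-test events lie wholly outside safety reporting. The passages just listed point towards capture; the accurate description is conflicting instructions.
- That the data monitoring committee cannot see such harm. Sections 5.2 and 5.3 leave routes to it that are not tied to randomisation.
- That a test-caused event has no valid causality category. It can be filed as unlikely or unrelated. The defect is that this files harm from a trial procedure as not trial-related.

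It is also fair that the secondary safety objective is an excess of adverse events over usual care. Events before randomisation cannot result from allocation, so starting the comparative data set at randomisation suits that objective and introduces no bias. This supports keeping pre-randomisation events out of the arm comparison. It does not support leaving them unrecorded.

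What the objection does not remove is that 5.1 is the only text that fixes a start for mandatory SAE recording, and that none of the other passages reliably fills the gap.

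**Conclusion.** The point holds as a contradiction with a safety consequence. Mandatory SAE recording begins at randomisation, the baseline graded exercise test comes after consent and before it, and Table 2 conflicts with that start. Section 5.1 also conflicts with section 5.3 on non-serious events. Serious events from the first of the four scheduled graded tests, including in people never randomised, are therefore not reliably captured. In addition, section 5.3.2 cannot identify an event in either arm as caused by a trial assessment.

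The conclusion rests on the inference that the graded test is among the functional assessments made before randomisation. The number of events affected cannot be estimated from the protocol. The comparison between arms and the primary analysis are unaffected. The change is worth making because it closes an oversight gap at little cost, not because a trial result is at risk.

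**What to change.** 1. Amend section 5.1 so that SAEs are recorded from informed consent to the last study visit, whether or not the person is later randomised. This agrees with the baseline entry in Table 2.
2. Reconcile sections 5.1 and 5.3 so that the protocol states once whether non-serious unexpected events are reported, and align the adverse event row of Table 2 with that statement.
3. In section 6.4, tabulate SAEs before randomisation separately, outside the arm comparison.
4. In section 5.3.2, assess relatedness to the exercise intervention or a trial assessment procedure, and record which of the two applies.

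The cost is a short text amendment, one eCRF field and a few more SAE forms. No assessment is added and the randomised comparison does not change.

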5.2 Unexpected Serious Adverse Events

SAEs should be reported to the Clinical Trials Unit within 7 days. The report should include an assessment of causality by the Principal Investigator at each site (see section 5.4). The Chief Investigator will be responsible for the prompt notification of findings that could adversely affect the health of subjects or impact on the conduct of the trial. Notification of confirmed unexpected SAEs will be to the Sponsor, the Research Ethics Committee and the Data and Safety Monitoring Committee (DSMC).

5.3 Reporting Unexpected Serious Adverse Events

Investigators will make their reports of all unexpected adverse events, whether serious or not, to the Glasgow Clinical Trials Unit.

5.3.1 Assessment of intensity

Mild: The subject is aware of the event or symptom, but the event or symptom is easily tolerated.

Moderate: The subject experiences sufficient discomfort to interfere with or reduce his or her usual level of activity.

Severe: Significant impairment of functioning; the subject is unable to carry out usual activities and/or the subject's life is at risk from the event

5.3.2 Assessment of causality

Probable: A causal relationship is clinically / biologically highly plausible and there is a plausible time sequence between onset of the adverse event and the exercise intervention.

Possible: A causal relationship is clinically / biologically plausible and there is a plausible time sequence between onset of the adverse event and the exercise intervention.

Unlikely: A causal relationship is improbable and another documented cause of the adverse event is most plausible.

Unrelated: A causal relationship can definitely be excluded and another documented cause of the adverse event is most plausible.

6. Statistical Considerations

Analysis and reporting of this trial will be based on Consolidated Standards of Reporting Trials (CONSORT) guidelines with the analyses conducted on an intention-to-treat basis. Descriptive statistics of clinical and socio-demographic variables at baseline will be presented. All treatment comparisons will be adjusted for the minimisation variables (diabetic status, age and gender).

6.1 Primary Outcome

KDQOL PCS: The control (UCHD) and intervention (EXHD) groups will be compared on the primary outcome measure (change from baseline to 6 months in KDQOL-SF 1.3 PCS) using a normal linear model adjusting for baseline KDQOL-SF 1.3 PCS. The findings will be presented as the (adjusted) mean difference (95% confidence interval) between the treatment groups

6.1 Secondary Outcomes

Other continuous outcomes will be analysed as for the primary outcome. Binary secondary outcomes will be compared between treatment arms using multiple logistic regression. The results will be presented as the adjusted odds-ratio for intervention versus control and its 95% confidence interval. Time to event secondary outcomes will be analysed using the Cox proportional hazards model to determine the adjusted hazard-ratio (95% confidence interval) for intervention versus control.

6.3 Exploratory Analysis

Each continuous outcome measured at multiple time points during the course of the trial (e.g. KDQOL PCS) will be analysed using a normal linear mixed model to evaluate how it evolves in the two arms over the course of the trial.

6.4 Safety Analyses

Discontinuations from the intervention and permanent study withdrawals and their reasons will be tabulated as will adherence to the intervention. Serious adverse events will be tabulated by system organ class and body system.

6.5 Interim Analysis

No formal interim analyses will be conducted. Unblinded safety data will be reviewed by an independent data monitoring committee to ensure the ongoing safety of participants.

6.6 Sample Size Calculation

A total of 380 patients will be randomised equally in the 5 centres to either UCHD or EXHD, giving 190 per treatment arm. Based on evidence from phase II trials (23) we expect 17-25% of patients to discontinue the exercise programme due to transplant, death or personal choice over the 9 month intervention period. A similar discontinuation rate will occur in the UCHD group, leading to 133 patients per group completing the study. Based on the PCS variability seen in Painter et al (31) and comparing 6-month KDQOL PCS between groups by two sample t-test (two-sided 5% significance level), this sample size would give 83% power to detect a mean difference of 4 points in KDQOL PCS. Greater power would be achieved in the final trial analysis through adjustment for baseline KDQOLPCS using analysis of covariance (ANCOVA). The 4 point effect size is of clinical relevance: as there is an established relationship between each 1 point increase in PCS and reduced mortality and hospitalisation (8,9). Such effect sizes have been reported for HD patients with a 7-point increase in the mean PCS of low functioning patients observed after an exercise training intervention (33).

7. Data Handling & Record Keeping

It is the responsibility of the PI (in conjunction with the Research Coordinator and RA) to ensure the accuracy of all data entered and recorded in the electronic CRFs and the database. The Delegation of Responsibilities Log will identify all trial personnel responsible for data collection, entry, handling and managing the database. The data will be collected by the RA (who will be blinded to the treatment allocation) and/or the RC, either directly onto a paper CRF with subsequent transcription to the eCRF, or direct data entry onto the web based eCRF. Where there is electronic storage of non-identifiable data it will be on a password protected device and/or database.

The study questionnaires (e.g KDQOL and EQ-5D) will be completed at each assessment visit by the patient with the assistance of the research assistant, directly onto a paper format with subsequent transcription to the eCRF.If the participant does not attend the assessment, the questionnaires will be given to the participant during dialysis, and collected back by the physiotherapy assistant.

NHS laboratory derived blood tests will be held on local NHS clinical systems databases in an identifiable format and for an indefinite time frame which can be assessed by primary and secondary care practitioners for future health care of patients. All research data and data established from the NHS tests will be stored in an unidentifiable format on password protected disaster recovery formatted database on the Glasgow Clinical Trial Unit server. Quality control of data will be maintained by

the Data Monitoring Committee. Patients will be informed of data storage and consent will be sought.

All research blood samples (link-anonymised) will be processed at each site and transported to the relevant laboratory for analysis. Depending upon volume and composition of each blood sample, additional blood serum/plasma samples will be stored (with consent.) and transported at the end of the study to the clinical laboratory at King's College Hospital under the custodianship of the CI for future research which will be scientifically and ethically reviewed. The medical notes will act as source data for past medical history, subsequent medical conditions, hospital admissions, diagnostic reports, and blood and urine results.

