
We propose to employ physiotherapy assistants (PA, band 4 technical Instructors) in each region to deliver the intra-dialytic intervention. All PAs will be trained by the joint PI and regional coordinators, on how to standardise the delivery of the exercise prescription as well as how to record exercise prescription milestones, compliance behaviours, and any adverse outcomes. The proposed exercise intervention delivered this way would ensure appropriate and consistently applied progression of both the duration and intensity of the exercise training. Recent evidence from the British Renal Society Symposium revealed that successful patient compliance with and the effectiveness of intra-dialytic exercise training was enhanced by the involvement of a physiotherapy assistant in programme delivery (34). This role, supervised and quality assured by the regional coordinator, involves the technical implementation of the exercise prescription and associated protocols produced by the regional Research Assistant who will be blinded to treatment allocation.

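### The protocol relies on blinded outcome assessment, but gives the blinded assessor the exercise prescriptions and lets the treating physiotherapy assistant collect the primary questionnaire from non-attenders

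*Protocol*

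**What the plan says.** **Safeguard.** Section 2.2 states that the treating physiotherapy assistants and the participants cannot be blinded, and "thus the study will undertake blinded outcome assessment and analysis". The synopsis and section 1.1 call the trial single-blind.

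**Delivery and prescription.** Section 4.5.2 says: "We propose to employ physiotherapy assistants (PA, band 4 technical Instructors) in each region to deliver the intra-dialytic intervention". The assistant implements "the exercise prescription and associated protocols produced by the regional Research Assistant who will be blinded to treatment allocation". The same section derives each prescription from the peak aerobic capacity test and raises it individually in months 2-4, 5-6 and 7-9. The assistant's role is "supervised and quality assured by the regional coordinator".

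**Outcome collection.** The opening text of section 7 says: "The data will be collected by the RA (who will be blinded to the treatment allocation) and/or the RC". Questionnaires are normally completed by the patient at the assessment visit with the RA's help. If the participant does not attend, "the questionnaires will be given to the participant during dialysis, and collected back by the physiotherapy assistant". KDQOL is one of these questionnaires, and the change in its physical composite score (PCS) at 6 months is the primary endpoint (section 2.1.3).

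**The concern.** In an open-label trial with a patient-reported primary endpoint, what remains of blinding depends on who runs the assessments and handles the forms. The protocol assigns those tasks in ways that do not fit section 2.2.

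- **An assessor who learns the allocation** can influence the tests that the assessor runs (peak aerobic capacity, sit-to-stand, timed-up-and-go), through encouragement or the judgement of end points. The same person could also influence KDQOL answers given with assistance.
- **A participant who returns a quality-of-life form to the person who trains them** may answer more favourably. Usual-care participants have no comparable relationship with the assistant, so any such shift would differ by arm.

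Analysis cannot reliably undo either effect once the data are collected. Roles are fixed in the protocol, so this is not a detail that can be left to the SAP.

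**Working it through.** No figure in the protocol settles this point, so the check sets the role statements side by side.

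| Role | Task in the intervention (4.5.2) | Task in outcome collection (7) | Blinding stated |
|---|---|---|---|
| Physiotherapy assistant | Delivers the exercise | Collects questionnaires from non-attenders | Cannot be blinded (2.2) |
| Research Assistant (RA) | Produces prescription and associated protocols | Collects outcome data; helps with KDQOL | Blinded (4.5.2 and 7) |
| RC (section 7) | None under this title; a regional coordinator supervises the assistants | May collect outcome data | None |

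**Step 1: the RA.** Only the exercise arm follows a prescription. Two workflows fit the text.
- *Workflow A:* the RA writes a prescription for every participant from the baseline test, before allocation is known, and the assistant does all later progression. The RA can stay blind. Section 2.2 places the baseline assessment before randomisation, and Table 2 schedules the aerobic test at baseline, so this is feasible.
- *Workflow B:* the RA writes or updates prescriptions after randomisation, for exercise participants only. The RA then knows the arm.

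The protocol does not choose between them. Section 4.5.2 describes individual increases to month 9 and names the RA as producer of the prescription without limiting that to baseline. Both the 6-month primary assessment and the 9-month assessment fall within or at the end of that period.

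**Step 2: the fallback route.** The form goes back through a person whom section 2.2 says cannot be blinded and whom section 4.5.2 has delivering exercise three times a week in one arm. No sealed return, neutral collector or record of route is specified.

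**Step 3: the RC.** Blinding is attached to the RA only. An outcome collector with no stated blinding does not meet section 2.2, whoever holds the role.

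**Step 4: can the effect be sized?** If a share f of exercise-arm 6-month forms comes by the fallback route, and those answers shift by b points with no shift in usual care, the bias in the mean difference is f × b. The protocol gives neither value. Under assumed values only:
- f = 10%, b = 2: 0.10 × 2 = 0.2 points, or 0.2/4 = 5% of the 4-point target in section 6.6;
- f = 20%, b = 4: 0.20 × 4 = 0.8 points, or 0.8/4 = 20%;
- f = 30%, b = 4: 0.30 × 4 = 1.2 points, or 1.2/4 = 30%.

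For scale, the stated 83% power at 4 points implies a standard error of about 4/(1.96 + 0.95) = 1.37 points, so 0.8 points is about 0.8/1.37 = 0.6 standard errors. The planned 133 completers of 190 per arm do not supply f: people lost to the study are not the people who miss a visit but still return a form. These lines show only how the bias would scale.

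**The case against.** The strongest reply is that nothing here proves unblinding. Four points in it deserve weight.

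- **The RA can stay blind.** Workflow A is compatible with the text. Section 4.5.2 has exercise adjusted by ratings of perceived exertion, which suggests session-level work, and credits delivery through the assistants with consistent progression. A reader might infer that the RA cannot work blind. The documents do not support that; they leave it open. The objection removes the certainty but not the gap, because the protocol never says that workflow A is intended.
- **The assistant only collects the form.** Section 7 does not say that the assistant hands it out or helps with it. A reader might infer that the therapist assists with the primary outcome; the text does not say so. The route is also confined to non-attenders, applies to both arms and reduces missing data. What stands is the unsealed return to one's own trainer.
- **Participants are unblinded anyway.** No choice of collector makes KDQOL a blinded outcome, and assessor blinding matters most for the assessor-run tests. That is correct, but it is no reason to add an avoidable arm-dependent influence.
- **The RC may not be the regional coordinator.** A reader might infer that the person supervising the exercise also collects outcomes. Section 7 says Research Coordinator, section 4.5.2 says regional coordinator, and the protocol never equates them. Only the missing blinding statement stands.

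A numerical bias claim would also be unsupported, because both inputs would have to be assumed.

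**Conclusion.** The point holds as a conflict between stated roles and the stated safeguard. Sections 2.2, 4.5.2 and 7 can be followed together only through a workflow that the protocol does not describe.

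- **RA conflict:** as written, producing individual prescriptions can reveal allocation to the person who collects outcomes. It mainly threatens the assessor-run tests and RA-assisted KDQOL. This rests on prescriptions being needed for the exercise arm only and on the absence of any rule that they are written for all before allocation.
- **Fallback conflict:** collection of KDQOL by the treating assistant invites response bias that differs by arm. The direction most to be expected favours exercise. The size cannot be estimated from the documents.
- **RC:** the missing blinding statement is a smaller gap of the same kind.

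The documents do not show that blinding would fail in practice or that the single-blind label is false. They show that its protection is not secured where it is needed.

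**What to change.** Reconcile the three sections.

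1. **Section 4.5.2.** Limit the RA to supplying exercise-test results, or a baseline prescription, for every participant in both arms before allocation is known. Assign all prescription work after randomisation to staff who do not assess outcomes. This concerns who does the work and leaves the content of the exercise programme unchanged.
2. **Section 7, collectors.** Require that anyone who runs assessor-led tests or assists with questionnaires is blinded and takes no part in delivering or supervising the intervention. Apply this to the RC as well, and state whether the RC and the regional coordinator are the same role.
3. **Section 7, fallback questionnaires.** Have them self-completed and returned in a sealed envelope, not through the treating physiotherapy assistant, by the same procedure in both arms. Do not send the RA into the dialysis unit to fetch them, because exercise is visible there. Unit staff are not blind either, so if they pass the envelope on, the protection comes from the seal and the identical procedure.
4. **Record the collection route** for each questionnaire and run a sensitivity analysis of the primary outcome by route. The analysis can be specified in the SAP, but the route must be captured at the time. Route is determined after randomisation, so this analysis is a check on robustness and not a replacement for the primary comparison.

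The cost is role wording in two sections, a procedure update, one extra data field and a small shift of tasks between existing staff. Anyone newly handling trial forms would need an entry on the delegation log (section 8.5).
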